#### 9.1.2 [With Day 29 markers]

If Day 29 markers are included, then participants in the immunogenicity subcohort and outcome cases will have marker data at Day 1, 29, 57. All immunogenicity analyses (graphical and tabular) of Day 57 markers are also conducted for Day 29 markers.

#### 9.1.3 Graphical description of antibody marker data

The Day 1, 57 antibody marker data collected from the immunogenicity subcohort participants will be described graphically. These data are representative of the entire study cohort. Importantly, only antibody data from the immunogenicity subcohort are included (i.e., no data from cases outside the subcohort are included). This makes the analyses unsupervised (independent of case-control status), enabling interrogation and optimization of the antibody biomarkers prior to the inferential correlates analyses.

Plots are developed for the following purposes. All of the analyses are done separately within each of the four subgroups defined by randomization arm cross-classified with baseline negative/positive status. In addition, many of the descriptive analyses will also be done separately for each demographic subgroup of interest listed above. For descriptive plots of individual marker data points that pool over one or more of the baseline strata subgroups, plots show all observed data points.

For each antibody marker readout, both Day 57 and baseline-subtracted Day 57 readouts are of interest. We will refer to the latter as 'delta.' All readouts, including delta, will be plotted on the  $\log_{10}$  scale, with plotting labels on the natural scale. As such, delta is  $\log_{10}$  fold-rise in the marker readout from baseline.

The following descriptive graphical analyses are done.

- 1. The distribution of each antibody marker readout at Day 1 and Day 57 will be described with plots of empirical reverse cumulative distribution functions (rcdfs) and boxplots (including individual data points) within each of the four groups defined by randomization arm (vaccine, placebo) and baseline positivity stratum (negative, positive). Inverse probability of sampling into the subcohort weights are used in the estimation of the rcdf curves; henceforth we refer to these weights ( $\hat{w}_{subcohort.57x}$ ) are used in the estimation of the rcdf curves; henceforth we refer to these weights as "inverse probability of sampling" (IPS) weights. Analyses of Day 1 markers always pool across vaccine and placebo recipients given that the two subgroups are the same at baseline.
- 2. Plots are arranged to compare each Day 57 marker readout between randomization arms within each of the baseline seropositive and baseline seronegative subgroups.
- 3. Plots are also arranged to compare each Day 57 marker readout between baseline serostatus groups within each randomization arm.
- 4. The correlation of each antibody marker readout between Day 1 and Day 57, and between Day 1 and delta, is examined within each of the baseline strata subgroups, and within each randomization arm and baseline positivity stratum. Pairs plots/scatterplots will be used, annotated with baseline strata-adjusted Spearman rank correlations, implemented in the PResiduals R package available on CRAN. For calculating the correlation

within each randomization arm and baseline positivity stratum, because PResiduals does not currently handle sampling weights, the correlation estimates are computed as follows: For each re-sampled data set in the second approach to graphical plotting, the covariate-adjusted Spearman correlation is calculated. The average of the estimated correlations across re-sampled data sets is reported.

- 5. The correlation of each pair of Day 1 antibody marker readouts are compared within each baseline positivity stratum, pooling over the two randomization arms. Pairs plots/scatterplots and baseline-strata adjusted Spearman rank correlations are used, with covariate-adjusted Spearman rank correlations computed as described above.
- 6. The correlation of each pair of Day 57 and delta antibody marker readouts are compared within each randomization arm within each baseline positivity stratum. Pairs plots/scatterplots and baseline-strata adjusted Spearman rank correlations are used, with covariate-adjusted Spearman rank correlations computed as described above.
- 7. Point estimates of Day 57 marker positive response rates for the vaccine arm by the baseline demographic subgroups and the baseline serostrata are provided, as well as pooled over baseline demographic strata. The point and 95% CI estimates include all of the data and use IPS weights.

#### 9.2 Methods for Positive Response Calls for bAb and nAb Assays

As noted above, binding antibody responders at each pre-defined timepoint are defined as participants with concentration above the specified positivity cut-off, with a separate cut-off for each antigen Spike, RBD, N (10.8424, 14.0858, and 23.4711, respectively, in BAU/ml).

Pseudovirus neutralization responders at each pre-defined timepoint are defined as participants who had baseline ID50 values below the LLOD with detectable ID50 neutralization titer above the assay LLOD, or as participants with baseline values above the LLOD with a 4-fold increase in neutralizing antibody titer. Otherwise a value is negative for pseudovirus neutralization. The same approach is used based on cID80 titer. Similarly, for the WT live virus-nAb MN50 marker, WT live virus neutralization responders at each pre-defined timepoint are defined as participants who had baseline MN50 values below the LLOQ with detectable MN50 above the assay LLOQ or as participants with baseline values above the LLOQ with a 4-fold increase in neutralizing antibody titer. Otherwise a value is negative for WT live virus neutralization.

#### 9.3 SARS-CoV-2 Antigen Targets Used for bAb and nAb Markers

The homologous vaccine strain antigens are used for the immune correlates analyses for the bAb markers, whereas the homologous vaccine strain with D614G mutation is used for the pseudovirus nAb markers.

#### 9.4 Score Antibody Markers Combining Information Across Individual bAb and/or nAb Readouts

Depending on the number and features of antigens that are selected for defining antibody marker variables, feature extraction/selection techniques may be employed to determine score/synthesis marker variables that are optimized according to some criterion that would reflect maximum signal-relevant diversity (e.g., He and Fong, 2019). In addition, the unsupervised dimensionality reduction techniques such as principal components analysis (PCA) and nonlinear extensions of PCA (e.g. FSDAM1 and FSDAM2; Fong and Xu, 2021) may also be used to define score variables that maximally capture the main immune response signal and to study whether there are more than one distinct signals that are associated with the outcome. If such synthesis features are defined, then they will be included as input features in the machine learning (superlearning) prediction modeling (multivariable CoR objective).

The purpose of the score markers is to seek to maximally capture the main immune response signal and to study whether score markers can provide strengthened association with outcome compared to the individual assay markers.

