Table 3: Potential Traditional Approval Requirements for a Day 57 Antibody Marker

Because CoPs can differ by study endpoint Plotkin (2010) and vaccine efficacy can differ by study endpoint, this criterion will not necessarily be important.

A potential goalpost for a *non-validated surrogate* for accelerated approval can be conceptualized as the same as that for traditional approval, with modifications:

- The package of evidence for the seven sources listed in Table 3 may be less stringent quantitatively, and not requiring success on all of the first six categories.
- Source 4 (Phase 3 CoR in vaccine recipients) would need to have strong evidence (highly statistically significant and highly predictive).
- The support for an immune correlate may be more restricted to a given study endpoint.
- It may no longer be required to have replication of results across two or more Phase 3 trials.

It is hypothesized that a single validated assay will yield a validated or nonvalidated surrogate endpoint, e.g., based on binding antibody IgG concentration or serum ID50 or cID80 titer to viruses pseudotyped with the Spike vaccine insert protein (or live SARS-CoV-2). However, the goalposts could potentially also be met by a synthesis biomarker aggregated from measurements from multiple validated assays if this aggregation substantially improves the correlate (e.g., a co-correlate Plotkin (2010); Plotkin and Gilbert (2018)). However, the preferred approach, for parsimony and practical utility, would be to define a correlates of protection as a single biomarker derived from a single assay.

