Table 7 lists the learning algorithms that are applied to estimate the conditional probability of the outcome based on the input variable sets considered above. Most of the algorithms are non-data-adaptive type learning algorithms, such as parametric regression models (e.g., generalized linear models [glms]), which are simple, stable, and advantageous for an application with a limited number of endpoint events. Data-adaptive type algorithms are also included if the number of endpoint events is high enough, for increasing flexibility of modeling and reducing the risk of model misspecification: SL.ranger, SL.gam, SL.polymars, and SL.xgboost. All of the selected learners are coded into the SuperLearner R package. Before fitting the superlearner models to the vaccine arm data, a decision will be made on how to define the "baseline risk factors" input variable set, based on prediction-accuracy results of the Superlearner analysis that built the baseline behavioral risk score based on the placebo arm, as well as on external knowledge of important individual risk factors. The set of baseline risk factors will include a subset of individual risk factors and/or the baseline risk score itself.

For the immune correlates objective the superlearner model is fit to each of the following 12 variable sets, with immunological variables listed in Section 12.6.2:

- 1. Baseline risk factors
- 2. Baseline risk factors and the Day 57 bAb anti-Spike markers
- 3. Baseline risk factors and the Day 57 bAb anti-RBD markers
- 4. Baseline risk factors and the Day 57 pseudovirus-nAb ID50 markers
- 5. Baseline risk factors and the Day 57 pseudovirus-nAb cID80 markers
- 6. Baseline risk factors and the Day 57 live virus-nAb MN50 markers
- 7. Baseline risk factors and the Day 57 bAb markers and the Day 57 pseudovirus-nAb ID50 markers
- 8. Baseline risk factors and the Day 57 bAb markers and the Day 57 pseudovirus-nAb cID80 markers
- 9. Baseline risk factors and the Day 57 bAb markers and the Day 57 live virus-nAb MN50 markers
- 10. Baseline risk factors and the Day 57 bAb markers and the combination scores across the five markers [PCA1, PCA2, FSDAM1/FSDAM2 (the first two components of nonlinear PCA), and the maximum signal diversity score He and Fong (2019)].
- 11. Baseline risk factors and all individual Day 57 marker variables
- 12. Baseline risk factors and all individual Day 57 marker variables and all combination scores (full model)

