Therefore in total, 12 variable sets are studied. The reason to include the first variable set is to investigate how much incremental improvement in predicting outcome is obtained by adding antibody marker variables on top of baseline demographic/exposure factors. The other variable sets are designed to compare the four immunoassay types by their predictiveness, to compare the two pseudovirus neutralization readouts ID50 and cID80 for their predictiveness, and to investigate incremental predictive value in using multiple immunoassays. The final variable set is included as the full model that considers all variables together, which serves as another reference model.

Table 7: Learning Algorithms in the Superlearner Library of Estimators of the Conditional Probability of Outcome, for Building the Baseline Risk Score Based on the Placebo Arm^1.

	Scroons/
	Screens
Algorithms	Tuning Parameters
SL.mean	None
$\mathrm{SL.glm}$	Low-collinearity and (All, Lasso, $LR)^2$
SL.bayesglm	Low-collinearity and (All, Lasso, LR)
SL.glm.interaction	Low-collinearity and (All, Lasso, LR)
SL.glmnet	(alpha=1; All)
SL.gam	Low-collinearity and (Lasso, LR)
SL.ksvm	Low-collinearity and (kernel="rbfdot", "polydot") and (Lasso, LR)
SL.polymars	Low-collinearity and (Lasso, LR)
$SL.xgboost^3$	All and $(maxdepth, shrinkage, balance) = (4, 0.1, no)$
SL.ranger 	All and balance $=$ no

All continuous and ordinal covariates are pre-standardized to have empirical mean 0 and standard deviation 1.

All = include all variables; Lasso = include variables with non-zero coefficients in the standard implementation of SL.glmnet that optimizes the lasso tuning parameter via cross-validation; Low-collinearity = do not allow any pairs of quantitative variables with Spearman rank correlation > 0.90; LR = Univariate logistic regression Wald test 2-sided p-value < 0.10.

 Covariate balancing (if requested) is done using option scale\_pos\_weight in SL.xgboost and option case.weights in SL.ranger.

Table 8: Learning Algorithms in the Superlearner Library of Estimators of the Conditional Probability of Outcome: Simplified Library in the Event of Fewer than 50 Vaccine Breakthrough Cases for an Analysis, for Use in Multivariable CoR Analysis of Moderna COVE.

	Screens/
Algorithms	Tuning Parameters
SL.mean	None
$\mathrm{SL.glm}$	Low-collinearity and (All, Lasso, $LR)^2$
SL.glmnet	(All, alpha=0) $(All, alpha=1)$

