## 12.6.6 Variable set and individual variable importance

The importance of variable sets (and individual variables) will be summarized by the estimated gain in population prediction potential (also referred to as the intrinsic importance) when comparing each variable set plus baseline risk factors to baseline risk factors alone. Prediction potential (predictiveness) will be measured using CV-AUC. Inference on the intrinsic importance will be based off sample splitting; thus, both the estimated variable importance and the estimated CV-AUC of each variable set when evaluated on independent data from the data used to evaluate the CV-AUC of the baseline risk factors will be reported. The class-balancing versions of SL.xgboost will be dropped from the Super Learner library in the variable importance computation as the regression carried out to account for the two-phase sampling will be based on a continuous outcome (so there won't be any imbalance).

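### No superlearner variable set holds the score markers without individual markers, so the plan lacks the direct comparison that Section 9.4 names as a purpose of the scores

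*Combined protocol and SAP*

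**What the plan says.** - **Purpose (Section 9.4).** One stated reason for the score markers is "to study whether score markers can provide strengthened association with outcome compared to the individual assay markers". The scores are optional, and their destination is the superlearner: "If such synthesis features are defined, then they will be included as input features in the machine learning (superlearning) prediction modeling".
- **Where they enter (Section 12.6.4).** Set 10 is "Baseline risk factors and the Day 57 bAb markers and the combination scores across the five markers". Set 12 is "Baseline risk factors and all individual Day 57 marker variables and all combination scores (full model"). Set 11, the closest neighbour of set 12, is "Baseline risk factors and all individual Day 57 marker variables". The list is closed: "Therefore in total, 12 variable sets are studied". Section 12.6.5 clones sets 2-12 for Day 29 and for Day 29 with Day 57, which gives 34.
- **Variable importance (Section 12.6.6).** Sets, and individual variables, are assessed by "comparing each variable set plus baseline risk factors to baseline risk factors alone". The individual variables are listed in Section 12.6.2, and no score is among them.
- **Use of the answer (Section 5).** A single marker from one assay is preferred, but the surrogate goalposts could also be met by a biomarker "aggregated from measurements from multiple validated assays if this aggregation substantially improves the correlate".

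**The concern.** Section 9.4 asks a score-versus-marker question: does an aggregate associate more strongly with outcome than a single assay readout? Answering it needs one model with the scores and without the individual markers, set against models with the individual markers. The variable sets seem to offer only mixtures.

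If so, two results could be misread. A higher CV-AUC for set 10 than for a single-assay set could come from the added Spike and RBD binding antibody (bAb) variables rather than from aggregation. A negligible gain of set 12 over set 11 could be taken as evidence against aggregation, when it only says that the scores add little once every individual marker is already in the model. Section 5 would accept a multi-assay biomarker only if aggregation clearly helps, and Section 16.1 gives the superlearner objective special weight in ranking markers. The comparison should therefore be readable from the output.

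**Working it through.** **1. Reproduce the counts.** Section 12.6.4 lists 12 sets. With Day 29, set 1 is common and sets 2-12 appear three times: 1 + 3 x 11 = 34. Both figures match the SAP.

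**2. Flag the sets** (every set also holds the baseline risk factors).

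| Set | Individual markers | Scores |
|---|---|---|
| 1 | none | no |
| 2-6 | one readout each: Spike, RBD, ID50, cID80, MN50 | no |
| 7, 8, 9 | Spike and RBD, plus ID50, cID80 or MN50 | no |
| 10 | Spike and RBD | yes |
| 11 | all five | no |
| 12 | all five | yes |

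Sets with scores: 2 of 12 (6 of 34 with Day 29: sets 10, 12, 21, 23, 32 and 34). Sets with scores and no individual marker: 0 of 12 and 0 of 34. By the variable list in Section 12.6.2 (4 + 4 + 8 + 4 = 20), set 10 mixes 4 + 4 = 8 bAb variables with 5 scores (PCA1, PCA2, FSDAM1, FSDAM2, maximum diversity), and set 12 mixes 20 individual variables with those 5.

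**3. Contrasts that remain.**
- Set 12 against 11 shows what the scores add to all individual markers. It is the only pair that differs solely in the scores.
- Set 10 against 7, 8 or 9 puts the scores in place of one neutralization readout, given bAb.
- Set 10 has no comparator holding only baseline factors with the Spike and RBD markers. Sets 7, 8, 9 and 11 hold both bAb markers without scores, but always with at least one neutralization readout.

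**4. Other analyses.** The univariable Cox tests cover the five individual markers (Section 12.4.2). The multivariable Cox models use RBD with ID50 and/or MN50 (Sections 12.7.3-12.7.4). The CoP analyses take the five markers one at a time (Sections 13 and 15). Section 14 mentions a marker score for the VE curve when closeout placebo vaccination data exist, but that score is derived within that method and is not one of the Section 9.4 scores.

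**5. Illustration.** Inputs from Section 24.2.1 (vaccine, baseline negative, Day 57): correlation 0.7, raised to 0.8 for Spike-RBD and 0.9 for ID50-cID80. Assumptions: 400,000 records, log odds ratio -0.8 per SD of the signal, about 1.5% risk, main-terms logistic models, PCA1 and PCA2 as the scores, no baseline factors, no input cap. AUC:

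| Risk driven by | Scores only | Best single marker | Set 7 | Set 9 | Set 10 | Set 11 | Set 12 |
|---|---|---|---|---|---|---|---|
| Common signal (PCA1) | 0.7103 | 0.6939 | 0.7078 | 0.7028 | 0.7104 | 0.7105 | 0.7105 |
| Spike alone | 0.6994 | 0.7126 | 0.7126 | 0.7126 | 0.7126 | 0.7126 | 0.7126 |
| MN50 alone | 0.6768 | 0.7074 | 0.6576 | 0.7075 | 0.7076 | 0.7076 | 0.7076 |

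- Scores only minus best single marker: 0.7103 - 0.6939 = +0.016; 0.6994 - 0.7126 = -0.013; 0.6768 - 0.7074 = -0.031.
- Set 12 minus set 11: 0.000 in all three rows, because PCA1 and PCA2 are linear in markers that set 11 already holds.
- Set 10 minus set 7 in the MN50 row: 0.7076 - 0.6576 = +0.050. The scores look helpful because they carry MN50 information that set 7 lacks, although scores alone fall below MN50 alone.

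In this setting the planned contrasts do not track the direct one.

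**The case against.** - **Contrasts do exist.** Set 10 against 7, 8 or 9 holds baseline factors and bAb fixed and swaps scores for a neutralization readout. This stands: a reader might infer that the plan says nothing about scores against individual markers, and that goes too far. What it offers is conditional on bAb.
- **Section 12.6.6 may already cover scores.** It speaks of individual variables, Section 12.3 calls the combinations synthesis markers, and Section 12.6.1 promises importance for each marker. On that reading each score would get its own model with baseline factors. But Section 12.6.2 lists no score, and set 12 names individual variables and combination scores separately. The text is ambiguous and should be settled.
- **Set 12 against 11 need not be zero.** The library includes penalized and tree-based learners, FSDAM is nonlinear, and a binding input cap means set 11 need not hold all five markers. This stands. The 0.000 belongs to uncapped, unpenalized main-terms models.
- **A scores-only set would not escape screening.** At the 35-case minimum in Table 4 the cap is floor(35/6) = 5 inputs. With the three default baseline factors of Section 10, five scores make 3 + 5 = 8 inputs, which needs 48 cases (48/6 = 8). This stands, so fitting under the cap is no argument for the added set.
- **Limited stakes.** Scores are optional, Section 5 prefers a single assay and describes its Table 3 requirements as conjecture, and no p-value or flag depends on scores. This stands and keeps the point modest.

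**Conclusion.** The point holds as a gap between a stated aim and the listed models. No variable set (0 of 12, or 0 of 34 with Day 29) compares the scores directly with individual markers, and no other analysis uses these scores. The conclusion rests on the enumeration. The AUC values only illustrate it under the stated assumptions and do not predict results with 35 to 50 cases.

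Three stronger readings are not supported. It is not true that no comparison of any kind is possible, since the incremental and substitution contrasts remain. It is not true that set 12 must equal set 11 under the full library. Nor is set 10 useless: it addresses scores given bAb, which is a legitimate but different question. The point assumes that individual variables in Section 12.6.6 means those listed in Section 12.6.2. If the authors meant to include scores, one sentence would close that part. This is a cheap improvement and does not threaten the validity of the correlates analyses.

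**What to change.** 1. Keep set 10. Add a variable set made up of the baseline risk factors and the combination scores, cloned to the Day 29 and the Day 29 with Day 57 blocks. This gives 13 sets, or 1 + 3 x 12 = 37 with Day 29.
2. Name the comparisons in Section 12.6.4: CV-AUC of the new set against sets 2-6 (scores versus single-assay markers) and against set 11 (the same assays, aggregated versus individual). The second is needed because the first mixes aggregation with access to more assays.
3. State in Section 12.6.6 that variable importance is also computed for each score alone with baseline factors, so that one score can be set beside one marker. The pooled set cannot show this.

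Cost: one extra superlearner run and one forest-plot row per time-point block, plus the per-score importance estimates, with no new p-values. The input cap and screens apply to the new set as to the others, so with few cases screening will partly decide which scores stay. The Prelude calls the SAP a work in progress, so the change can be made before case status is unblinded.
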